Data Analysis for Drug Repurposing for Effective Alzheimer's Medicines – Pentoxifylline vs Cilostazol

NCT05635370

July 7, 2023

1. Comparison Details

a. Intended aim(s)

To evaluate the comparative risk of dementia onset between patients treated with Pentoxifylline versus cilostazol for peripheral artery disease (PAD).

b. Primary endpoint

Incident dementia (i.e., Alzheimer's disease, vascular dementia, senile, presenile, or unspecified dementia, or dementia in other diseases classified elsewhere).

2. Person responsible for implementation

[name]

3. Data Source(s)

Medicare, 2008-2018

4. Study Design Diagrams

[figure not shown]
[figure not shown]

Figure- Alternate analysis approaches

[figure not shown]
■■■ Included person-time
 ■■■ Excluded person-time

Provides 'on treatment' estimates for the outcome risk and addresses exposure person-time misclassification

Analysis 1

[figure not shown]

Analysis 3

[figure not shown]

Addresses reverse causation due to preferential treatment initiation related to unrecorded cognitive impairment at study start and informative-censoring

Analysis 2

Analysis 4

5. Cohort Identification

a. Cohort Summary

This study will employ a new user, active comparator, observational cohort study design comparing Pentoxifylline versus Cilostazol. The patients will be required to have continuous enrollment during the baseline period of 365 days before initiation of study drugs (cohort entry/index date). Follow-up for the outcome (dementia) differs between analyses. Follow-up begins the day after drug initiation (analysis 1, 3, 4); 180 days after drug initiation (analysis 2).

b. Key details regarding cohort creation

Index date:

- Day of initiation of new Pentoxifylline versus Cilostazol use

Inclusion criteria for analyses 1, 3, 4:

- Aged \geq 65 years on the index date
- 365 days enrollment in Medicare Parts A, B, and D with no HMO coverage prior to index date
- No use of Pentoxifylline versus Cilostazol, any time prior to index date (all available lookback approach with a minimum of 365 days)
- No diagnosis of dementia any time prior to and including index date
- No history of nursing home admission recorded in any time prior to and including index date
- At least two claims with peripheral artery disease diagnosis recorded in 365 days prior to index date (ICD-9 or ICD-10 codes)¹

Inclusion criteria for analysis 2:

- Aged \geq 65 years on the index date

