- 365 days enrollment in Medicare Parts A, B, and D with no HMO coverage prior to index date
- No use of Pentoxifylline versus Cilostazol, any time prior to index date (all available lookback approach with a minimum of 365 days)
- No diagnosis of dementia any time prior to and including index date
- No history of nursing home admission recorded in any time prior to and including index date
- At least two claims with peripheral artery disease diagnosis recorded in 365 days prior to index date (ICD-9 or ICD-10 codes)¹

- 180-day continuous use of Pentoxifylline versus Cilostazol starting on the index date

c. Flowchart of the study cohort assembly

	Less Excluded Patients	Remaining Patients
All patients		23,466,175
Did not meet cohort entry criteria	-23,393,311	72,864
Excluded due to insufficient enrollment	-45,683	27,181
Excluded based on Dementia Exclusion	-6,100	21,081
Excluded based on Nursing Home Admission	-4,080	17,001
Excluded based on Peripheral artery disease Diagnosis	-4,524	12,477
Excluded anyone aged <65 at index	-2,079	10,398
Patients in Pentoxifylline group		1,701
Patients in Cilostazol group		8,697
Final cohort		10,398

6. Variables

a. Exposure-related variables:

Study drug:

The study exposure of interest is initiation of Pentoxifylline

Comparator:

Cilostazol

b. Covariates:

Demographics	
Age	Region
Gender	Calendar year of index date
Race	Low income subsidy

Dementia risk factors	
Diabetes	Depression
Obesity	Anxiety
Hypertension	Bipolar disorder
Coronary artery disease	Schizophrenia

Markers for healthy behavior, frailty, healthcare use	
Smoking	Number of hospitalizations
Mammography	Number of physician office visits
Colonoscopy	Number of serum creatinine tests ordered
Fecal occult blood test	Composite frailty score
Influenza vaccination	Number of C-reactive protein tests ordered
Pneumococcal vaccination	Osteoporosis
Herpes zoster vaccination	Fractures
Bone mineral density test	Falls
Number of distinct generic agents	Use of supplemental oxygen
Number of emergency room visits	Combined comorbidity score
Number of outpatient visits	

Comedication use	
Lithium	Diuretics
Anti-epileptic mood stabilizers	Nitrates
Anti-epileptics (other than mood stabilizers)	Lipid lowering drugs

Atypical antipsychotics	Non-insulin diabetes medications
Benzodiazepines	Insulin
Serotonin-norepinephrine reuptake Inhibitors	Antidepressants
Selective serotonin reuptake inhibitors	Angiotensin II receptor blockers (ARBs)

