Tricyclic antidepressants (TCAs)	Angiotensin converting enzyme inhibitors (ACEi)
Typical antipsychotics	Calcium channel blockers
Anticoagulants	Beta blockers
Antiplatelet agents	

Comorbid conditions	
Atrial fibrillation	Chronic liver disease
Coronary artery disease	Asthma
Heart failure	Ischemic heart disease
Stroke or transient ischemic attack	Chronic obstructive pulmonary disease
Peripheral vascular disease	Malignancy
Hyperlipidemia	Drug or alcohol abuse or dependence
Renal dysfunction	Venous thromboembolism
Rheumatoid Arthritis	Hypertension

Other PAD treatments and PAD severity indicators	
Critical limb ischemia Thrombolytic therapy (streptokinase, urokinase, alteplase, tissue plasminogen activator (tPA), pro-urokinase, reteplase, tenecteplase and Staphylokinase)	Number of cardiologist visits Number of hospitalizations with PAD

ICD-9, ICD-10, HCPCS, and NDC codes used to define the covariates listed above are available in Appendix A.

c. Outcome variables and study follow-up:

- **Primary outcome:** incident dementia, i.e., Alzheimer's disease, vascular dementia, senile, presenile, or unspecified dementia, or dementia in other diseases classified elsewhere. Outcome will be defined by 1 inpatient

claim or 2 outpatient claims in analysis 1, 2, 3. In analysis 4, the outcome will be defined by 1 inpatient or 1 outpatient claims and 1 prescription claim for a symptomatic treatment [donepezil, galantamine, rivastigmine, and memantine] within 6 months of each other with outcome date assigned to second event in the sequence.

- Secondary outcomes: Individual component:

Alzheimer's disease

Condition	ICD-9 and ICD-10 codes
Alzheimer's disease	331.0*, F00*, G30*
Vascular dementia	290.4*, F01*
Senile, presenile, or unspecified dementia	290.0*, 290.1*. 290.3*, 797*, F03*
Dementia in other diseases classified elsewhere	331.1*, 331.2*, 331.7*, 294.1*, F02*

For analysis 1,3, and 4 the follow-up will start the day after initiation of Pentoxifylline and Cilostazol and will continue until the earliest date of the following events:

- The first occurrence of the outcome of interest
- The date of end of continuous registration in the database,
- End of the study period,
- Measured death event occurs,
- The date of drug discontinuation, defined as the date of the last continuous treatment episode of the index drug (Pentoxifylline and Cilostazol) plus a defined grace period (i.e., 90 days after the end of the last prescription's days' supply in main analyses).

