For analysis 2, the follow-up will start 180 days after initiation of Pentoxifylline and Cilostazol and will continue until the earliest date of the following events:

- The first occurrence of the outcome of interest, unless otherwise specified for selected outcomes,
- The date of end of continuous registration in the database,
- End of the study period,
- Measured death event occurs,
- Maximum allowed follow-up time (1095 days) reached

7. Propensity score analysis

We will use a propensity-score (PS)²-based approach to account for measured confounding in this study. The PS will be calculated as the predicted probability of initiating the exposure of interest (i.e., the repurposing candidate) versus the reference drug conditional on baseline covariates using multivariable logistic regression constructed separately in each data source. On average, patients with similar PSs have similar distribution of potential confounders used to estimate the PS. Therefore, analyses conditioned on the PS provide effect estimates that are free from measured confounding. For all our analyses, initiators of each exposure of interest will be matched with initiators of the reference exposure based on their PS within each data source.³ Pair matching will be conducted using a nearest-neighbor algorithm, which seeks to minimize the distance between propensity scores in each pair of treated and reference patients,⁴ and a caliper of 0.025 on the natural scale of the PS will be used to ensure similarity between the matched patients.⁵

We report multiple diagnostics for PS analysis in this protocol. First, the PS distributional overlap is provided between two groups before and after matching to ensure comparability of these groups.⁶ Next, balance in each individual covariate between two treatment groups is reported using standardized differences.⁷

8. Table for covariate balance

Variable	Crude			PS-Matched		
	Pentoxifylline (N = 1,701)	Cilostazol (N = 8,697)	St. Diff	Pentoxifylline (N = 1,687)	Cilostazol (N = 1,687)	St. Diff
Demographics						
Age, mean (SD)	76.2 (7.3)	75.3 (6.9)	0.13	76.2 (7.2)	76.3 (7.2)	-0.01
Gender, n (%)						
Male	828 (48.7)	4733 (54.4)	-0.12	822 (48.7)	827 (49)	-0.01
Female	873 (51.3)	3964 (45.6)	0.12	865 (51.3)	860 (51)	0.01
Race, n (%)						
White	1386 (81.5)	7096 (81.6)	0.00	1377 (81.6)	1347 (79.8)	0.05
Black	156 (9.2)	935 (10.8)	-0.05	156 (9.2)	176 (10.4)	-0.04
Hispanic	70 (4.1)	237 (2.7)	0.08	67 (4)	65 (3.9)	0.01

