Number of hospitalizations, mean (SD)	0.3 (0.7)	0.2 (0.6)	0.09	0.3 (0.7)	0.3 (0.6)	0.01
Number of outpatient visits, mean (SD)	15 (10.6)	13.1 (8.6)	0.20	14.8 (10.1)	14.9 (10)	-0.01
Number of serum creatinine tests ordered, mean (SD)	1.6 (2.7)	1.5 (2.3)	0.01	1.6 (2.7)	1.5 (2.2)	0.02
Composite frailty score, mean (SD)	0.2 (0.1)	0.2 (0.1)	0.21	0.2 (0.1)	0.2 (0.1)	0.02
Falls, n (%)	107 (6.3)	472 (5.4)	0.04	107 (6.3)	108 (6.4)	0.00
Fractures, n (%)	141 (8.3)	591 (6.8)	0.06	139 (8.2)	138 (8.2)	0.00
Osteoporosis, n (%)	247 (14.5)	1051 (12.1)	0.07	242 (14.3)	239 (14.2)	0.01
Use of supplemental oxygen, n (%)	26 (1.5)	150 (1.7)	-0.02	26 (1.5)	23 (1.4)	0.02
Combined comorbidity score, mean (SD)	3.4 (2.8)	2.9 (2.4)	0.18	3.3 (2.7)	3.4 (2.6)	-0.02
Comedication use, n (%)						
Angiotensin converting enzyme inhibitors (ACEi)	646 (38)	3657 (42)	-0.08	643 (38.1)	641 (38)	0.00
Angiotensin II receptor blockers (ARBs)	488 (28.7)	2519 (29)	-0.01	485 (28.7)	482 (28.6)	0.00
Antidepressants	435 (25.6)	2046 (23.5)	0.05	430 (25.5)	416 (24.7)	0.02
Beta blockers	894 (52.6)	4801 (55.2)	-0.05	887 (52.6)	884 (52.4)	0.00
Calcium channel blockers	593 (34.9)	3243 (37.3)	-0.05	588 (34.9)	590 (35)	0.00
DMARD	86 (5.1)	212 (2.4)	0.14	80 (4.7)	81 (4.8)	0.00
Diuretics	930 (54.7)	4251 (48.9)	0.12	918 (54.4)	925 (54.8)	-0.01
Insulin	228 (13.4)	1176 (13.5)	0.00	224 (13.3)	216 (12.8)	0.01
Lipid lowering drugs	1169 (68.7)	6557 (75.4)	-0.15	1161 (68.8)	1151 (68.2)	0.01
Nitrates	239 (14.1)	1355 (15.6)	-0.04	233 (13.8)	225 (13.3)	0.01

DREAM study protocol - Comparison 12 Pentoxifylline vs Cilostazol

Non-insulin diabetes medications	477 (28)	2493 (28.7)	-0.01	473 (28)	481 (28.5)	-0.01
Anticoagulants	218 (12.8)	814 (9.4)	0.11	212 (12.6)	190 (11.3)	0.04
Anti-epileptic mood stabilizers	20 (1.2)	94 (1.1)	0.01	20 (1.2)	17 (1)	0.02
Antiplatelet agents	411 (24.2)	8697 (100)	-2.51			0.00
Atypical antipsychotics	25 (1.5)	102 (1.2)	0.03	25 (1.5)	22 (1.3)	0.02
Benzodiazepines	352 (20.7)	1416 (16.3)	0.11	347 (20.6)	331 (19.6)	0.02
Lithium	2 (0.1)	14 (0.2)	-0.01			0.00
Anti-epileptics (other than mood stabilizers)	459 (27)	2073 (23.8)	0.07	455 (27)	457 (27.1)	0.00
Serotonin-norepinephrine reuptake inhibitors	83 (4.9)	361 (4.2)	0.04	82 (4.9)	75 (4.4)	0.02
Selective serotonin reuptake inhibitors	222 (13.1)	1141 (13.1)	0.00	221 (13.1)	221 (13.1)	0.00
Tricyclic antidepressants (TCAs)	77 (4.5)	320 (3.7)	0.04	75 (4.4)	63 (3.7)	0.04
Typical antipsychotics	8 (0.5)	20 (0.2)	0.04	8 (0.5)	10 (0.6)	-0.02

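### The antiplatelet covariate appears to count cilostazol itself: every comparator patient is positive, the matched difference of 0.00 cannot be real, and other antiplatelet use is not shown to be adjusted for

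*Combined protocol and SAP*

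**What the plan says.** Section 6b lists "Antiplatelet agents" under comedication use. It does not say that cilostazol is removed from the class. It states that the "codes used to define the covariates listed above are available in Appendix A", and that appendix is not part of the supplied text.

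Section 5a sets baseline as the 365 days before initiation. Section 5b requires no study-drug use "any time prior to index date (all available lookback approach with a minimum of 365 days".

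Section 7 estimates the PS by logistic regression on the baseline covariates and matches pairs within a caliper of 0.025 for all analyses. It says that "analyses conditioned on the PS provide effect estimates that are free from measured confounding", and that "balance in each individual covariate between two treatment groups is reported using standardized differences".

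In section 8 the crude part of the row is "Antiplatelet agents 411 (24.2) 8697 (100) -2.51". The matched counts for this row are blank and the matched standardized difference is printed as 0.00.

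**The concern.** A comedication present in exactly 100% of one arm and about a quarter of the other is not describing comedication. The count of 8,697 equals the whole comparator arm in the flowchart ("Patients in Cilostazol group 8,697"). New users of cilostazol have no earlier cilostazol fill, so the flag on every one of them most plausibly comes from the index fill. That would put cilostazol on the antiplatelet code list and the index date inside the covariate window.

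Two consequences follow. First, the variable as coded duplicates treatment assignment in the cilostazol arm and cannot serve as a confounder. Second, the quantity that the plan meant to control, use of other antiplatelet agents in patients with peripheral artery disease, is not visible anywhere. Vascular dementia is part of the primary outcome, so a difference between arms in other antiplatelet treatment could bias the hazard ratios. A reader who scans the last column for imbalance would see 0.00 and move on.

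**Working it through.** **Inputs** (all from the section 8 table; the caliper is from section 7)

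- Crude: 411 of 1,701 pentoxifylline and 8,697 of 8,697 cilostazol initiators are users.
- Group sizes: "Pentoxifylline (N = 1,701) Cilostazol (N = 8,697) St. Diff Pentoxifylline (N = 1,687) Cilostazol (N = 1,687) St. Diff".
- Caliper: 0.025 on the PS scale.

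**1. Reproduce the plan's crude figure.** For a binary covariate, d = (p1 − p2) / √{[p1(1 − p1) + p2(1 − p2)] / 2}.

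- p1 = 411/1,701 = 0.2416 and p2 = 1.
- d = −0.7584 / √(0.1832/2) = −0.7584/0.3027 = −2.505, which agrees with the printed −2.51.

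The formula also reproduces other rows:

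| Row | Printed | Recomputed |
|---|---|---|
| Critical limb ischemia, crude | 0.29 | 0.291 |
| Smoking, crude | −0.19 | −0.193 |
| Anticoagulants, matched | 0.04 | 0.040 |
| Influenza vaccination, matched | 0.06 | 0.058 |

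A few matched rows differ by one unit in the second decimal (for example colonoscopy: −0.015 recomputed, −0.02 printed). This does not matter here.

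**2. What the matched value has to be.** Every cilostazol initiator is a user, so all 1,687 matched ones are. Matching drops 1,701 − 1,687 = 14 pentoxifylline patients, so between 411 − 14 = 397 and 411 users remain.

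- 411 retained: p1 = 411/1,687 = 0.2436; d = −0.7564 / √(0.1843/2) = −2.49.
- 397 retained: p1 = 397/1,687 = 0.2353; d = −0.7647 / √(0.1800/2) = −2.55.

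A value of 0.00 needs equal prevalence. Both arms at 100% would need 1,687 pentoxifylline users, and only 411 exist. Both at 0% would need no cilostazol users, and all are users. No matched sample drawn from this cohort can give 0.00. The largest matched difference printed for any other row is 0.06.

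**3. Whether the variable could have been in the PS.** Non-users number 1,701 − 411 = 1,290, and all are on pentoxifylline. In a logistic PS with this term, their fitted score tends to 1. Among users the average score is 411/(411 + 8,697) = 0.045. A non-user would need a cilostazol patient with a score of about 0.975 or more to match within 0.025. In practice only the 411 pentoxifylline users could be matched, so about 411 pairs at most.

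The table reports 1,687 pairs, of which at least 1,687 − 411 = 1,276 contain a pentoxifylline non-user. An illustrative simulation, assuming one additional normal covariate shifted by 0.5 SD between arms, gave 411 pairs with the term and 1,700 without it. The row as coded was therefore not an effective PS term.

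**4. Possible size of the bias.** The prevalence of other antiplatelet use in the cilostazol arm (p0) is not in the documents, nor is its association with dementia (RR). Both are assumed. The multiplier on the hazard ratio is approximately [1 + p1(RR − 1)] / [1 + p0(RR − 1)], with p1 = 0.242.

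| Assumed p0 | RR | Multiplier |
|---|---|---|
| 24.2% (equal) | any | 1.00 |
| 35% | 1.2 | 1.0484/1.070 = 0.98 |
| 35% | 0.9 | 0.9758/0.965 = 1.01 |
| 50% | 1.5 | 1.121/1.250 = 0.90 |
| 50% | 0.8 | 0.9516/0.900 = 1.06 |
| 15% | 1.5 | 1.121/1.075 = 1.04 |

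Neither the size nor the direction can be settled from the documents.

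**The case against.** The strongest defence has four parts.

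*The 0.00 is probably a placeholder.* Schizophrenia and lithium also show blank matched counts beside 0.00, so the figure may mark rows not tabulated after matching. This is plausible, and blank cells alone are not an error. But the printed figure sits in the column that readers use to judge balance, carries no footnote, and cannot be true for this row. Small-cell suppression is an unlikely reason: matched counts of 4, 5 and 6 are printed elsewhere, and the cells here hold at least 397 and 1,687.

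*Leaving an exposure-defining variable out of the PS is correct, and a cilostazol-free version may exist.* The first half is right: this coding should not be in the model. The second cannot be excluded without Appendix A, and for the same reason the counting of the index fill is an inference. However, no replacement variable is described or shown.

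*Related variables are balanced.* Coronary and ischemic heart disease, stroke or transient ischemic attack, critical limb ischemia, cardiologist visits, hyperlipidemia, lipid-lowering drugs and anticoagulants all have matched differences of 0.04 or less in absolute value. This stands, and it may shrink the bias below the range above, which makes no allowance for it.

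*The table covers one cohort.* It describes the 10,398 patients in the flowchart, which has no 180-day continuous-use step. No separate balance table is given for analysis 2, so the problem there is expected from the shared covariate definition and not shown directly.

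These points temper the likely size of the bias. They do not supply the missing adjustment or make the printed balance figure valid.

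**Conclusion.** The concern holds, and the row is wrong as written. Three results need only the printed counts: the variable as coded separates the arms, it cannot have been an effective PS term with 1,687 pairs matched, and its matched standardized difference lies between −2.55 and −2.49, not at 0.00. That range describes a miscoded variable; it does not measure the imbalance in actual antiplatelet treatment, which is unknown.

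That the index cilostazol fill is being counted is a strong inference, since exactly every comparator patient is flagged and earlier use is excluded. As documented, a covariate the plan chose to control is neither adjusted for nor checked, so section 7's statements on balance and on measured confounding fail for it. Under the assumed inputs the effect on the hazard ratio runs from none to about 10%, and it may be smaller once the matched vascular covariates are considered.

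**What to change.** 1. Redefine the covariate as antiplatelet agents other than the study drugs by removing cilostazol from the code list, and say so in section 6b and Appendix A.
2. Assess it strictly before the index date, so that the index fill cannot count. Check the other comedication lists for study-drug codes.
3. Include the redefined variable in the PS model, re-match, and report its actual matched counts and standardized difference. Do the same for the analysis 2 cohort.
4. Where a matched cell is withheld or not tabulated, mark it as such instead of printing 0.00. This applies to schizophrenia and lithium as well.

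If a cilostazol-free variable was already used in the PS, naming it and showing its matched row would answer the adjustment point.

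The cost is a code-list edit and a re-run of PS estimation, matching, the balance table and the analyses that use the matched sample. No new data are needed. The number of matched pairs may change.
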